PROTOCOL TITLE: Hózhó (Heart Failure OptimiZation at Home to Improve Outcomes)
Trial for HF Patients Receiving Care through the Indian Health Service in Navajo Nation

Version Date 9/6/2022

Clinicaltrials.gov Registration # NCT05792085

Protocol Synopsis

TITLE	Hózhó (Heart Failure OptimiZation at Home to Improve Outcomes) Trial for HF Patients Receiving Care through the Indian Health Service in Navajo Nation
SPONSOR	University of Pennsylvania and Indian Health Service
FUNDING ORGANIZATION	Indian Health Service Quality Improvement Innovation Award
NUMBER OF SITES	1 (Gallup Service Unit)
RATIONALE	
Heart failure morbidity and mortality disproportionately impact racial minorities, and inequitable care delivery based on race is pervasive in the United States. The American Indian/Alaska Native (AI/AN) population is one of the populations that suffers most from health disparities. AI/AN patients with heart failure receiving care through the IHS (IHS) face tremendous barriers to accessing quality care, particularly specialized cardiac care. Guideline-directed recommended therapy (GDMT) can significantly lower mortality, hospitalizations and improve quality of life in heart failure with reduced ejection fraction (HFrEF). However, GDMT utilization rates are low nationally. AI/AN patients are at particular risk of not receiving appropriate GDMT. Innovative models to improve uptake of GDMT may help improve quality of care in this patient population.
 
Models that incorporating telemonitoring and strategies to support primary care physicians could be implemented to reach AI/AN patients with HFrEF that face barriers to accessing quality cardiovascular care, particularly those that receive care through the IHS, the federal healthcare agency responsible for providing medical and public health services to this population. A strategy to identify HFrEF patients and get them on appropriate therapy with telemonitoring should be evaluated through a pragmatic clinical trial as a strategy to ensure high-quality heart failure care for AI/AN patients,

	especially those living remotely and receiving care through the IHS, where cardiology care is often unavailable. The proposed pragmatic clinical trial aims to improve the quality of care of AI/AN patients with heart failure with reduced ejection fraction receiving care through the IHS. We will perform a pragmatic trial clinical that will use a stepped wedge randomized design to implement and evaluate the effectiveness of a strategy that leverages the electronic medical record to find HFrEF patients not on appropriate therapy, and initiates/optimizes GDMT through telemonitoring in the Navajo Nation.
STUDY DESIGN	This is cluster stepped wedge randomized control trial, with randomization at the patient level
PRIMARY OBJECTIVE	To evaluate if there is an increase in rates of guideline-directed medical therapy with implementation of the heart failure telemonitoring model
SECONDARY OBJECTIVES	To evaluate if there is an increase in the dose of the guideline-directed medical therapy with implementation of the heart failure telemonitoring model
NUMBER OF SUBJECTS	80-100 HFrEF patients
SUBJECT SELECTION CRITERIA	
Inclusion Criteria: This care delivery model will be applied to adult patients (age >18 years) with heart failure with reduced ejection fraction seen cared for in the Gallup Service Unit in Navajo Nation (Gallup Indian Medical Center and Tohatchi Helath Center) with at least 1 clinical encounter in past 12 months (including telemedicine), and has 1 active prescription at an IHS pharmacy in the last 12 months
 
Exclusion Criteria: Anyone not willing to participate, anyone that their primary care physician opts out as feels is inappropriate to participate, anyone on hospice care.

EFFICACY EVALUATIONS	
PRIMARY ENDPOINT	The proportion of patients who have an increase in the number of prescribed evidence-based therapies for HFrEF (beta-blockers, ACE-I/ARB/ARNI, MRA, SGLT2i) at 30 days post implementation. This endpoint is based on filling of the prescription.
SECONDARY ENDPOINTS	Secondary outcomes will include: percentage of patients prescribed each medication class (i.e. percentage on beta-blockers, percentage on ACE-I/ARB, percentage of ARNIs, percentage on SGLT2i, and percentage on MRAs), medication doses (all at 30-days as well as post-implementation at 6 months); HF hospitalizations at each time point, 6-month mortality, referrals, cardiac procedures, adverse events (to include hypokalemia [K<3.0

	mEq/L], hyperkalemia [K >5.5 mEq/L], AKI [defined as Cr increase >0.5 from baseline], Hyponatremia [Na<130 mg/dl], volume overload [urgent clinic visit/ ER visits for lower extremity edema, dyspnea, with clinical evaluation consistent with volume overload], hypotension (SBP <90mmHg), bradycardia (HR <50 bpm). Outcomes determined by review of medical, hospital, and billing records.
OTHER EVALUATIONS	None
SAFETY EVALUATIONS	Adverse events (to include hypokalemia [K<3.0 mEq/L], hyperkalemia [K >5.5 mEq/L], AKI [defined as Cr increase >0.5 from baseline], Hyponatremia [Na<130 mg/dl], volume overload [urgent clinic visit/ ER visits for lower extremity edema, dyspnea, with clinical evaluation consistent with volume overload], hypotension (SBP <90mmHg), bradycardia (HR <50 bpm).
PLANNED INTERIM ANALYSES	At 30-days after implementation for cluster 1, we will evaluate for safety. Serious adverse events will be monitored by the research team on an ongoing basis throughout the study.
STATISTICS Primary Analysis Plan	To assess the effectiveness of our intervention, measurement of rates of GDMT, including each specific medication of ACE inhibitors, ARB, ARNI, beta-blockers, MRA, SGLT2 inhibitors will be performed at baseline, at each cross-over time point, and at the conclusion of 6 months after the implementation of the intervention. The main analysis of our stepped wedge design will be based on a logistic mixed-effects model which will contain a random intercept to account for between-cluster variability, a fixed effect parameter for time, and a group indicator variable for the treatment for each subject and time to capture treatment differences over time.
Rationale for Number of Subjects	We anticipate there is approximately 100 patients with HFrEF actively engaged in care at GIMC. Our goal to enroll all patients given ethical concerns with withholding implementation to all patients.

SECTION 1: BACKGROUND

Statement of Purpose:

Heart failure is the leading cause of hospitalization among older adults and has a 5-year mortality of up to 50%.^{[1][2]} There are well-established evidence-based guidelines for treating heart failure with reduced ejection fraction (HFrEF), a major subset of HF. The background of guideline-directed medical therapy (GDMT) for HFrEF now includes 4 classes of therapy: a beta-blocker, an angiotensin-converting enzyme inhibitor (ACE) inhibitor/angiotensin receptor blocker (ARB) or preferably an angiotensin receptor-neprilysin inhibitor (ARNI), a mineralocorticoid receptor antagonist (MRA), and a sodium glucose transporter 2 (SGLT2) inhibitor ^[3-7]. There is a cumulative risk reduction for mortality of >75% among HF patients receiving combined therapy with a beta-blocker, ARNI, MRA and SGLT2 inhibitor.^[3] Therefore, the American College of Cardiology/American Heart Association guidelines recommend treatment with all 4 of these agents and titration to highest-tolerated dose (or target dose) to maximize clinical benefit.^[8] However, despite clear evidence-based interventions for HF, suboptimal care is a major driver of poor HF-related outcomes in the U.S.^[9] Guideline-directed therapies for HFrEF are underutilized among all patients in the U.S.^[10]. AI/AN patients receiving care through the Indian Health Service, in particular, are at high risk of not receiving appropriate GDMT given barriers to accessing appropriate care.^[11]

The reasons for underutilization of appropriate GDMT in HF are multifactorial. In the Indian Health Service, access to cardiology care is severely limited, and HF care is provided primarily by primary care providers. We surveyed primary providers at two Indian Health Service sites to identify the primary barriers to getting HFrEF patients on appropriate GDMT. The primary barriers identified were include lack of knowledge/comfort among providers about guidelines and appropriate management, clinical burden, time constraints during the visit. Given this we hypothesized that a model that identified HFrEF patients not on appropriate therapy, and initiated missing recommended therapy by the study team would be an effective way to improve HF quality of care and uptake of GDMT. In addition, given the rurality of the Navajo patients cared for at these two IHS sites, and the barriers to accessing care, we hypothesized that a telemonitoring model in which patients had GDMT initiation and uptitration at home, with home BP monitoring would be preferable.

We therefore, in discussion with community members and primary providers at two IHS sites in Navajo, designed a model to identify HFrEF patients cared for in the system, identify gaps in their therapy, and initiate appropriate therapy by the study team with home BP and HR monitoring for initiation and titration of GDMT. We propose a stepped wedge randomized trial to compare the implementation of this model compared to usual care over a 6 month period with 5, 30-day cross over periods. The primary outcome for the trial will be the proportion of patients who have an increase in the number of prescribed evidence-based therapies for HFrEF (beta-blockers, ACE-I/ARB/ARNI, MRA, SGLT2i) 30 days post implementation. This endpoint is based on filling of the prescription. In addition to addition of missing GDMT, we will also consider a change from an ACEI/ARB to an ARNI consistent with increase in the ‘number’ of GDMT given their demonstrated benefit. Secondary outcomes will include: percentage of

patients prescribed each medication class (i.e. percentage on beta-blockers, percentage on ACE-I/ARB, percentage of ARNIs, percentage on SGLT2i, and percentage on MRAs), medication doses, all at 30-days as well as post-implementation at 6 months; HF hospitalizations at each time point, 6-month mortality, adverse events (to include hypokalemia [$K < 3.0$ mEq/L], hyperkalemia [$K > 5.5$ mEq/L], AKI [defined as Cr increase > 0.5 from baseline], Hyponatremia [$Na < 130$ mg/dL], volume overload [urgent clinic visit/ ER visits for lower extremity edema, dyspnea, with clinical evaluation consistent with volume overload]. Outcomes determined by review of medical, hospital, and billing records.

2 STUDY RATIONALE

Treatment with GDMT for HFrEF with the 4 classes of recommended therapy significantly reduces heart failure hospitalization and overall mortality [3-8]. However, these therapies are underused among all patients nationally, but particularly among marginalized patient groups and racially minoritized patients, which is one of the factors that drives racial disparities in cardiovascular outcomes. Therefore, strategies to engage with marginalized patient groups in order to increase rates of recommended therapy are critically needed to improve cardiovascular outcomes and reduce disparities. American Indians are one of the most marginalized patient groups in the United States and the majority receive care through the Indian Health Service, where cardiology care is not readily available. Therefore, this study will evaluate if a model that leverages the electronic medical record to get American Indian patients with heart failure on appropriate therapy, and supports primary care providers with telemonitoring, is an effective way to ensure high-quality heart failure care for American Indian patients receiving care through the Indian Health Service in Navajo Nation.

2. 1 Risk/Benefit Assessment

This study will evaluate the effectiveness of a heart-failure care delivery model to improve rates of guideline recommended medical therapy through a stepped wedge randomized control trial. Therefore, the primary objective of this study is to evaluate if the implemented model is effective in increasing rates of medications that are already recommended by guidelines. All patients will only be started on medication after chart review by the research team which includes a cardiologist. Thus, patients will be started on appropriate therapy, as strongly recommended by current American College of Cardiology/American Heart Association Guidelines [4][8]. Since this model is being tested through a stepped wedge trial as a way to improve standard of care for heart failure patients, this study represents minimal risk to participants. The benefit is significant as increased use of guideline-recommended therapy and these medications has been demonstrated to reduce heart failure hospitalization and mortality

3. STUDY OBJECTIVES

3.1 Primary Objective

The primary objective is to assess the clinical efficacy of a heart failure care delivery model as measured by the rates of patients with an increase in the number of classes of rates of guideline directed medical therapy over the study period.

3.2 Secondary Objectives

The primary objective is to assess the clinical efficacy of a heart failure care deliver model as measured by the change in rates of each GDMT therapy, the doses of each therapy, differences in HF hospitalizations, referrals, cardiac interventions, and adverse events over the study period.

4. STUDY DESIGN

4.1 Study Overview

This is a single ‘center’ (Gallup Service Unit- which includes two ambulatory clinics), stepped wedge cluster randomized design with 5 clusters planned. We will randomize each patient to 1 of 5 clusters, each of which has a different enrollment time point, separated 1 month apart. Each patient will receive intervention with the heart failure care delivery model at time of enrollment. Evaluations will be taken at each cross-over time point and at conclusion of 6 months. Screening data will be reviewed to determine subject eligibility. Subjects who meet all inclusion criteria and none of the exclusion criteria will be entered into the study. Prior to enrollment for each patient, a message will be sent in that patient’s chart through the EHR to the patient’s primary provider who has 7 days to opt out if they think patient should not be enrolled.

Probable Duration of Project: Total duration of subject participation will be 6 months.

4.2 Study Setting

This study is being conducted at the ambulatory clinics in the Gallup Service Unit at Gallup Indian Medical Center (GIMC) and Tohatchi Health Center. GIMC is located in Gallup, New Mexico and is a 99-bed hospital that serves the Navajo Nation, the largest U.S. Indian tribe [12]. GIMC is part of the Indian Health Service-which is a federally-funded agency within the U.S. Department of Health and Human services, is responsible for providing health services to AI/AN patients. GIMC. has one of the highest clinical volumes in the IHS—250,000 outpatient encounters and 5800 inpatient admissions annually—and the largest staff of all Navajo IHS facilities. GIMC is associated with a primary care ambulatory clinic. With a 50-mile radius catchment area, it serves as the major Navajo referral hospital and ambulatory clinic for the Navajo Nation [13][14]. Tohatchi, is a smaller health center located 45 minutes north of GIMC, in a more rural remote area on the Navajo Nation, in Tohatchi, NM.

4.3 Study Design

Stepped-wedge designs are increasingly being utilized to evaluate interventions within routine care and are recommended where there are limited numbers of clusters [13]. In this study, we will perform a prospective stepped-wedge randomized control trial, where randomization will occur at the patient level with 5 patient clusters.

The randomization procedures will be managed independently at the University of Pennsylvania Cardiovascular Outcomes, Quality, and Evaluative Research Center. Physicians will be randomized through a SAS-based computer-generated randomization scheme developed by the study PI. Using a stepped-wedge design, each patient cluster will begin the study as a control

site, providing treatment as usual to participants (Control). Clusters will then progressively commence the heart failure care delivery model and will begin contributing to the intervention arm of the study in a stepped fashion (Intervention; see **Figure 1**). An independent statistician at University of Pennsylvania Cardiovascular Outcomes, Quality, and Evaluative Research Center will randomly generate the clusters and the order of the patient cluster. CONSORT procedures will be followed including using an intention to treat analysis.

Figure 1: Stepped-Wedge Implementation of HF Care Delivery Model

Stepped Wedge Design

[figure not shown]

Figure 1. Stepped wedge randomized controlled study design. Participants in the control condition will receive treatment as usual. Participants in the intervention condition will receive the heart failure care delivery model as described below. The patient clusters and order of intervention will be randomly allocated.

4.4. Randomization

Randomization in this study will occur at the level of the patient. This is a stepped wedge trial design, and patients will be randomized to 1 of 5 clusters. Every cluster will have the model implemented, but the time point of implementation will vary based on cluster, in 30 day increments. Cluster 1 will have the model implemented at time 0, cluster 2 at 30 days, cluster 3 at 60 days, etc (as shown in Figure 1). Prior to implementation, patients in pre-implementation time points will receive usual care. In addition, all providers received a lecture regarding updated ACC/AHA/HFSA guidelines and expert consensus prior to implementation of the model. Given the stepped-wedge design, all patients will eventually benefit from implementation of the model, but it also allows us to evaluate the effect of secular trends towards better care over time (and ensure the model rather than trends in care are not responsible for improving care).

5. CRITERIA FOR EVALUATION

5.1 Primary Efficacy Endpoint

The primary outcome for the trial will be the proportion of patients who have an increase in the number of prescribed evidence-based therapies for HFrEF (beta-blockers, ACE-I/ARB/ARNI, MRA, SGLT2i) 30 days post implementation. This endpoint is based on filling of the prescription. In IHS pharmacies, we are able to differentiate between active prescriptions that are filled/picked up, and those that are “not picked up”. We will only include filled prescriptions in the primary and secondary endpoints. In addition to addition of classes of GDMT, we will also consider a change from an ACEI/ARB to an ARNI consistent with increase in the ‘number’ of GDMT given their demonstrated superior benefit.[5]

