11. STATISTICAL METHODS AND CONSIDERATIONS

Prior to the analysis of the final study data, a detailed Statistical Analysis Plan (SAP) will be written describing all analyses that will be performed. The SAP will contain any modifications to the analysis plan described below.

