11.3. Analysis of Primary and Secondary Endpoints

To assess the effectiveness of our intervention, measurement of rates of GDMT, including each specific medication of ACE inhibitors, ARB, ARNI, beta-blockers, MRA, SGLT2 inhibitors will be performed at baseline, at each cross-over time point. The main analysis of our stepped wedge design will be based on a logistic mixed-effects model which will contain a random intercept to account for between-cluster variability, a fixed effect parameter for time, and a group indicator variable for the treatment for each subject and time to capture treatment differences over time.

Safety and tolerability data will be summarized by intervention group.

Adverse event rates will be coded by body system and MedDra classification term. Adverse events will be tabulated by treatment group and will include the number of patients for whom the event occurred, the rate of occurrence, and the severity and relationship to newly started therapy.

Statistical Analysis: The primary analysis will utilize the intention to treat principle. A generalized linear model will be used to assess the relationship between randomization cluster status and the primary outcome. The model will use a log-link and independent correlation structure to allow for calculation of adjusted risk ratios. Statistical significance will be based on a P value of <0.05. For categorical secondary outcomes, a similar generalized linear modeling approach will be used. For continuous secondary outcomes, a generalized linear model will be used.

Assessment of contamination: Providers may learn to better treat heart failure as consistent with evidence-based therapies over time. Given we are not clustering by provider, but rather patients, it is possible that providers will take what is being implemented on their patient that is in an active implementation phase, and apply it to a patient in a non-active implementation phase. Therefore, there is a high risk of contamination. However, with the stepped wedge design, we will be able to also see how GDMT rates increase over the study period for those clusters who are not immediately in an active implementation arm. We will be able to better understand if increases in GDMT are related to the intervention or just due to increases over time due to improved knowledge of providers over time.

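### The primary endpoint has no scoring rule for usual-care time, and its two models are not ranked; read literally, one of them contains no usual-care comparison

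*Combined protocol and SAP*

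**What the plan says.** **Endpoint.** Section 5.1 gives the "proportion of patients who have an increase in the number of prescribed evidence-based therapies for HFrEF (beta-blockers, ACE-I/ARB/ARNI, MRA, SGLT2i) 30 days post implementation". The synopsis has the same anchor, "at 30 days post implementation. This endpoint is based on filling of the prescription", and so does section 1. A switch from ACE-I/ARB to ARNI counts as an increase.

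**Schedule and data.** Section 4.4 implements the model in cluster 1 at time 0 and in each further cluster at 30-day steps, with usual care until then. All five clusters are eventually treated. Sections 9.1.1 and 11.3 record medications at baseline or enrolment and at each cross-over.

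**First model.** The synopsis and section 11.3 say: "The main analysis of our stepped wedge design will be based on a logistic mixed-effects model". Its terms for clustering and calendar time are listed as "a random intercept to account for between-cluster variability, a fixed effect parameter for time". The exposure in this model is described separately, as "a group indicator variable for the treatment for each subject and time to capture treatment differences over time".

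**Second model.** Later in section 11.3, under the primary analysis: "A generalized linear model will be used to assess the relationship between randomization cluster status and the primary outcome". Link, correlation and effect measure are settled in the sentence after it: "The model will use a log-link and independent correlation structure to allow for calculation of adjusted risk ratios".

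**Later document.** Section 11 promises that "a detailed Statistical Analysis Plan (SAP) will be written describing all analyses that will be performed", before the final study data are analysed. That document is not among those supplied.

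**The concern.** The trial's question is whether the care model raises GDMT use above usual care. That needs an outcome scored the same way in both conditions and one model that contrasts them.

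The endpoint is anchored to implementation, so a patient still in usual care has no stated 30-day window and no stated starting count. The two models differ in link, effect measure, correlation structure, named time term and exposure. The one tied by name to the primary outcome uses the cluster to which the patient was randomised. In a stepped wedge that gives the timing of treatment, not whether the patient is treated.

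If these choices are made after outcome data have been seen, the primary result is not prespecified. If the second model is run as written, it does not estimate the effect of the intervention.

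**Working it through.** **1. Which intervals have a defined outcome?** Inputs: 5 clusters, 30-day steps, cluster 1 at time 0 (section 4.4); 20 patients per cluster (section 11.4). Five clusters by five intervals give 25 cells.
- First 30 days after implementation: 5 cells, 100 patient-intervals. Endpoint defined.
- Usual care: 0+1+2+3+4 = 10 cells, 200 patient-intervals. Endpoint not defined.
- Later intervention time: 10 cells, 200 patient-intervals. Not covered by the 30-day endpoint.

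**2. Does the missing reference count matter?** Assume a chance h of an added class per 30 days of usual care, with additions kept. At day 120, a rolling 30-day reference gives h. A day-0 reference gives 1 − (1 − h)^4. For h = 5%, 10% and 20% that is 18.5%, 34.4% and 59.0%. The documents give no h; the range only shows that the rule must be named.

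**3. The second model read literally.** There is one outcome per patient, 30 days after implementation, with cluster as exposure. The risk ratio for cluster k is p_k / p_1, and all five p's are post-implementation rates. With an equal effect and no trend it is 1.00, whether the common rate is 5% or 50%. In a simulation (1,000 runs, 5 clusters of 20, 4-df test across clusters), rejection was 4.7% at assumed control and treated rates of 25% and 50%, 5.3% at 10% and 35%, and 5.0% at 10% and 60%. That is the nominal 5% level. A secular rise of 3 points per interval alone took it to 8.0%. With interval treatment status and interval effects instead, and control intervals scored, power at 25% against 50% was 98.9% (intervals simulated as independent within patient).

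**4. Different effect measures.** At 25% against 50%, the odds ratio is (0.50/0.50)/(0.25/0.75) = 3.0 and the risk ratio is 0.50/0.25 = 2.0.

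**5. Repeated intervals.** Illustration: identity link, unit cell variance, all 25 cells, period indicators, independence estimation.
- Let d be the cell's treatment indicator minus its period mean. The treated fractions are 1/5 to 5/5, so Σd² = 5 × (0.16 + 0.24 + 0.24 + 0.16 + 0) = 4.0. The naive variance is 1/4.0 = 0.250.
- The cluster sums of d are 2, 1, 0, −1, −2, whose squares total 10. With within-patient correlation ρ, the true variance is [(1 − ρ) × 4 + ρ × 10]/16.
- True over naive is 1 + 1.5ρ: 1.15, 1.45 and 1.75 at ρ = 0.1, 0.3 and 0.5.

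**6. Which post-crossover intervals enter?** In the same layout, one on/off indicator gives intervals 1 to 5 after crossover the weights 0.50, 0.30, 0.15, 0.05 and 0. With assumed rates of 5% in control and 50% in the first 30 days (difference 45 points), later rates of 10%, 50% or 60% give a coefficient of 25, 45 or 50 points.

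If only control and first intervals are used, period j has 6 − j cells, one of them treated. Then Σd² = 0.80 + 0.75 + 0.667 + 0.50 + 0 = 2.717 and the variance is 0.368. The standard-error ratio to pooling is √(0.368/0.250) = 1.21. With generalised least squares at ρ = 0.3 it is √(0.3334/0.2655) = 1.12.

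**7. The plan's own power figure.** Section 11.4 has 4 clusters, 5 time points, 20 per cluster, 25% to 50%. Here Σd² = 4 × (0.1875 + 0.25 + 0.1875) = 2.5, and the variance is (0.375 × 0.625/20)/2.5 = 0.00469, so SE = 0.0685. Power is Φ(0.25/0.0685 − 1.96) = 95.5%. The stated figure above 95% is reproduced at zero cluster correlation, but it concerns being on one therapy, not the primary endpoint, so it does not settle this point.

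**The case against.** **A control window can be built.** Fills are recorded at every cross-over, section 4.4 identifies usual-care time, and section 11.3 intends to look at GDMT rates in clusters not yet active. This stands: the data exist. The rule for using them does not.

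**Treated patients do have a baseline.** Section 4.1 gives each cluster its own enrolment point with intervention at enrolment, and section 9.1.1 records baseline medications then. Together these suggest a pre-implementation baseline, and this largely stands. A reader might infer that all patients are measured from day 0, giving clusters 1 to 5 spans of 30 to 150 days. The documents do not say so. Section 6.2, which enrols patients before placing them in a cluster, only leaves the date unclear.

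**The cluster exposure may be loose wording.** Section 4.3 describes clusters moving from control to intervention, and the first model already has a treatment indicator. That is possible, so a reader should not conclude that the trial will be analysed without a control comparison. But section 8.2 uses nearly the same phrase for the patient's assignment, so the literal reading is fair and the text needs correcting.

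**Silence is not absence.** The GLM's risk ratios are to be adjusted, and time may be among the unnamed adjusters. The mixed model's indicator may be meant to vary with time since crossover. Independence structure is often paired with robust errors, and naive errors are not stated. All this stands, so steps 5 and 6 show sensitivity, not demonstrated bias. A reader might also apply the familiar inflation 1 + 4ρ for five intervals. That belongs to a contrast between whole clusters, not to the treatment coefficient. With only control and first intervals and period indicators, the ratio in step 5 is 1.00.

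**A SAP is promised.** It is due only before the final analysis, whereas section 11.3 plans an interim look 30 days after the first cohort. The commitment helps, but does not show that these choices are fixed in advance.

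**Conclusion.** The point holds on the text in two respects: usual-care intervals have no scoring rule for the primary outcome, and two different models are given without a ranking. A third holds on the literal reading only: the GLM tied to the primary outcome cannot estimate intervention against usual care, and its expected risk ratios are 1.00 if the effect is equal across clusters and there is no trend.

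The variance understatement of about 1.15- to 1.75-fold is conditional on all five intervals entering, period effects, independence estimation, naive errors and an assumed correlation of 0.1 to 0.5. It comes from an identity-link illustration, whereas the plan's links are logit and log. The documents give no 30-day rate of an increase and no correlation, so the size and direction of any effect on the result are unknown. The layout assumes that cluster 1 has no usual-care interval. Section 4.4 implies this, section 4.3 has every cluster start as control, and Figure 1 is not shown.

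**What to change.** 1. **Outcome.** Score each 30-day interval in both conditions as an increase if the filled-class count at the end exceeds that at the start, counting an ACE-I/ARB to ARNI switch. State the enrolment date that serves as baseline.
2. **Models.** Name one model as primary and the other as sensitivity. Replace the cluster exposure in the GLM by the interval's control or intervention status. Put period effects in both. Use patient-clustered standard errors in the GLM and a patient random intercept in the mixed model.
3. **Intervals.** State which post-crossover intervals enter the primary contrast. The first 30 days alone match the stated endpoint, but cost about 12% to 21% in standard error if the effect is constant. With period indicators, cluster 5's intervention interval also gets no weight, because no controls remain. This is the sponsor's choice; report the other version as sensitivity.
4. **Timing.** Write this into the protocol or the promised SAP before outcome data are examined.

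The cost is wording and a little analysis work, with no added patients or visits. As a guide to the first-30-days option, take section 11.4's 25% to 50% (a different outcome), zero correlation and variance 0.368 × 0.2344/n. SE is 0.0657 with 20 per cluster and 0.0734 with 16 (80 patients over five clusters), so power is about 97% and 93%. The latter is below the plan's 95%.
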